Hypothesis: We hypothesize that: relative to the control group, the PLASMA group will report greater improvement over time in (H1) quality of life (primary outcome), and (H2) asthma knowledge, attitudes, outcome expectations, self-efficacy, self-management skills, and asthma control, FEV1 (exploratory outcomes). (H3) The post-PLASMA scores on outcome measures will be higher than pre-program scores from both treatment groups.

- 2) To examine the mediating effects of the secondary outcomes (knowledge, attitudes, outcome expectations, self-efficacy, self-management skills, asthma control, and FEV1) on the primary outcome (quality of life) of the intervention.
- 3) To examine the moderating effects of personal factors (e.g., age, sex, family support) on primary and secondary outcomes of the intervention.
- 4) To evaluate the effects of PLASMA on primary and exploratory outcomes in peer leaders (16-20 years).

Hypothesis: We hypothesize that the peer leaders (n=42) will report significant improvement in quality of life (primary outcome) and secondary outcomes (knowledge, attitudes, outcome expectations, self-efficacy, self-management skills, asthma control and FEV1) over the course of 15 months.

- 5) To determine the economic impact of the intervention. This aim will be accomplished by (5a) measuring the direct healthcare costs and total costs of the PLASMA program, as compared with the control group; (5b) performing net cost analyses for each type of costs; and (5c) estimating cost-effectiveness ratios of the PLASMA group compared with the control.

Hypothesis: We hypothesize that the direct and overall costs per participant in the PLASMA group will be less than costs per participant in the control group, or cost neutral.

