4. METHODS AND STUDY PROCEDURES

4.1 Study Procedures and Assessments

Design: This study will use a two-group randomized controlled design implemented in three metropolitan cities: Buffalo, NY, Baltimore, MD, and Memphis, TN. The project coordinator and a research assistant in each city who are not involved in direct patient care of teens with asthma will be responsible for recruitment and consent process taking place in each site. Peer leaders will attend a three-day intense training session that will take place prior to camps, lead small-group instructional activities at a one-day camp (PLASMA group) and follow up their group members bimonthly for 15 months. Camp participants from each site (n=126) will be randomly assigned to the peer-led (PLASMA) group or the adult-led (control) group. Upon enrollment, participants will be stratified by gender and age (younger 12-14 years, older 15-17 years), and randomly assigned to either group within each of four blocks generated by the combination of gender and age strata. Each group will attend a separate day camp where an asthma self-management program will be implemented either by peer leaders (intervention) or healthcare professionals (control). After the camp, the intervention group will receive peer-leader contacts bimonthly for 14 months using phone calls or other communication technologies (e.g., emails, or short-message system (e.g., texting) of teens' choice. Adult instructors (healthcare professionals) will contact the control group bimonthly for 14 months using similar methods, but different contact topics.

Both groups (intervention and control – more details below) will provide data at enrollment (T1), 3 months later (T2), immediately following the camp (T3), and at 3-, 6-, 9-, 12-, and 15-months post-camp (T4-T8).

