(j) Peak Expiratory Flow Rate (PEFR): we will use commercial electronic peak flow meters (Piko-1™). The Piko-1 (Ferraris Respiratory, Louisville, CO, USA) measures peak expiratory flow and FEV1, and it can store up to 96 measurements that are date- and time- stamped. Three color zones are visible on the display of the device: green for >80%, yellow for 50-80% and red for <50% of an individual's best. Stored data in the Piko-1 can be downloaded to a computer. The device is powered by batteries, lasting about 2 years if used 6 times a day. Values from the Piko-1 have shown high correlations ($r=0.93-0.95$) with those from a reference spirometer, indicating

the acceptable accuracy of the device.^{50, 51} The Piko-1 will be provided to 20 randomly selected participants from each site (10 from each treatment group) who will be instructed to use the device at least once a day. The RAs will make home visits every 3 months to download the stored data to a computer. For the rest of the sample, we will provide a manual peak flow meter with training on its use and instruct them to use it daily and record the values in a log as we proposed in the application, because this is part of self-management routines that we will attempt to reinforce through our training programs.

(k) Spirometry will be performed using a portable KoKo® spirometer (Pulmonary Data Service; Louisville, CO). Predicted values will be based on the equations of Polgar. The primary variables will be forced vital capacity (FVC) and FEV1, to be measured twice, at the camp and 15-months post-camp. Respiratory therapists at each site will be trained to perform the test in accordance with the ATS/ERS standardization of spirometry⁵² prior to conducting the tests, and data will be interpreted in collaboration with a pulmonologist at the study center.

Moderators:

(l) Perceived Family Support (PFS): We found that family support influenced quality of life and asthma control in adolescents.⁵³ This 20-item scale measures individuals' perception of their family fulfilling their needs for support, information and feedback. Construct and criterion validity was demonstrated.⁵⁴ Cronbach's α in our previous study was .85. **(m) Sociodemographic Form (SDF)** will be completed by parents to indicate adolescents' race, age, sex, insurance type, parental education and annual family income.

Table 1: Study measures for each assessment point

PRIMARY OUTCOME	PAQL	EXPLORATORY OUTCOMES												MODERATOR	

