10. DATA ANALYSIS AND DATA MONITORING

10.1 Planned Statistical Analysis: Analyses will be performed using SAS, and R⁵⁶ will be used as analysis software to ensure the validity and reproducibility of the results. We will perform descriptive statistics on each outcome measure to look for abnormality and outliers. If a measure is not normally distributed, transformation will be applied. We will identify and investigate outliers for sources of errors, and conduct preliminary analyses on data distribution and bivariate correlations to determine the appropriate statistical model as well as the final interpretation of the results. We will investigate missing data with pattern analysis for data missing completely at random (MCAR), missing at random (MAR) or missing not at random (MNAR), and use statistical methods appropriate for each type such as maximum likelihood and multiple imputation to impute missing values so full analysis can be performed with sensitivity. We will compute Cronbach's alphas for psychometric measures, and assess construct validity using exploratory or confirmatory factor analysis when appropriate. The PLASMA and control groups will be compared on baseline data to determine any systematic differences; if any are found, analyses will include the variables as covariates in the model to adjust for the imbalances.

Aim 1: A multi-site hierarchical three-level linear mixed-effects model,^{26, 56, 57} where level 1 represents repeated measures, level 2 = subject, and level 3 = site, will be used to analyze treatment differences and treatment-by-time interaction described in the following notation by Hedeker and Gibbons.⁵⁷

Aim 2: The mediating effects will be examined mainly using the mediation methods of Baron & Kenny.⁵⁸ When found significant, a multiple mediation analysis⁵⁹ procedure will be used to further determine whether the effect of PLASMA on quality of life is mediated jointly by multiple exploratory outcomes.

Aim 3: Moderating effects will be examined by multiple linear models and generalized linear models described in Berridge and Crouchley⁵⁶ or Chen and Peace⁶⁰ along with the above multi-site hierarchical three-level linear mixed-effects models.

Aim 4: This aim will be tested by applying the multi-site hierarchical two-level linear mixed-effects models described in the analysis for Aim 1, with level 1 representing longitudinal measurements and level 2 sites.

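### Aim 2 states no baseline adjustment, and the plan's only covariate rule, triggered by imbalance between arms, does not address confounding of the mediator-to-quality-of-life path

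*Combined protocol and SAP*

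**What the plan says.** Section 10.1 gives Aim 2 two sentences. The first is "The mediating effects will be examined mainly using the mediation methods of Baron & Kenny". The second adds that, if the result is significant, "a multiple mediation analysis" follows, to see whether several exploratory outcomes jointly carry the effect. Neither sentence names covariates, a baseline adjustment, a change score or a visit.

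The only covariate rule in Section 10.1 is a general one. The two arms are first checked against each other at baseline. The action that follows concerns only the differences this check turns up: "if any are found, analyses will include the variables as covariates in the model to adjust for the imbalances".

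Section 1 lists seven mediators: knowledge, attitudes, outcome expectations, self-efficacy, self-management skills, asthma control and FEV1. The outcome is quality of life (PAQOL). Of family support, Section 4.1 item (l) says "We found that family support influenced quality of life and asthma control in adolescents", yet family support is planned only as a moderator (Aim 3). Section 4.1 places two assessments, T1 and T2, before the camp.

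**The concern.** Randomisation protects the treatment-to-mediator and treatment-to-outcome comparisons. It does not protect the third regression, quality of life on mediator given treatment. A teen with high self-efficacy and good quality of life before the camp will tend to have both afterwards in either arm. Checking balance between arms does not detect this, because the confounding acts within arms.

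Family support shows the problem in the plan's own terms: by the protocol's account it influences a listed mediator and the outcome, and under the imbalance rule it would usually stay out of the model.

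At stake is the conclusion about how PLASMA works. A mediator that PLASMA raises, and that merely correlates with quality of life between teens, could be reported as the mechanism. The multiple-mediation step names no covariates either, so it would inherit the same paths.

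**Working it through.** **Figures from the plan.** Aim 2 has no sample size, power or error rate of its own. The nearest figure reproduces: 276 / (1 - 0.27) = 378.1, matching the stated 378. I use N = 276, split 1:1, with two-sided alpha 0.05 (the plan gives .05 without sidedness).

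**How often the imbalance rule acts.** For three balanced baseline variables (mediator, quality of life, family support), each tested independently at 0.05, the chance that at least one is flagged is 1 - 0.95³ = 14.3%. In simulation it was 13-15%. About 86% of trials would therefore enter none of them.

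**Assumptions (none from the documents).** PLASMA raises the mediator by a = 0.4 SD. The mediator has no effect on quality of life. One follow-up visit is analysed, with raw scores. Stable traits plus independent visit noise give a mediator-outcome correlation r of 0.2-0.4 and a visit-to-visit correlation s of 0.5-0.7.

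**Bias in the mediator path b, middle case r = 0.3, s = 0.6** (unit variances within arm):
- Unadjusted: b = r = 0.30. Spurious indirect effect = a × b = 0.4 × 0.30 = 0.12 SD.
- Adjusted for T1 mediator and T1 quality of life: the mediator's coefficients on these are (0.6 - 0.3 × 0.3)/0.91 = 0.560 and (0.3 - 0.3 × 0.6)/0.91 = 0.132. Residual covariance with the outcome is 0.3 - 0.560 × 0.3 - 0.132 × 0.6 = 0.053. Residual variance is 1 - 0.560 × 0.6 - 0.132 × 0.3 = 0.624. So b = 0.053/0.624 = 0.085 (simulation 0.083).
- Adjusted for T1/T2 means (variance (1 + 0.6)/2 = 0.8): coefficients are 0.39/0.55 = 0.709 and 0.06/0.55 = 0.109. So b = (0.3 - 0.213 - 0.065)/(1 - 0.425 - 0.033) = 0.022/0.542 = 0.040. Indirect effect = 0.4 × 0.040 = 0.016 SD.

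Across the grid the unadjusted b equals r, so the bias is 0.2 to 0.4 SD per SD.

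**False mediation, simulated over the same grid:**

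| Criterion | Unadjusted | T1/T2 means |
|---|---|---|
| Two paths significant, no effect of PLASMA on quality of life | 83-92% | 4-34% |
| Total effect also significant, no effect of PLASMA on quality of life | about 4-5% | lower still |
| Total effect also significant, direct effect 0.35 SD | about 70-78% | about 6-34% |

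If the direct effect must also shrink once the mediator is entered, the 4-5% becomes about 2-3%.

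**A second model.** Here the baseline mediator, baseline quality of life and family support carry all the confounding. Scenarios are weak, medium and strong (stability 0.3/0.5/0.6; baseline mediator-outcome correlation 0.2/0.3/0.5; family-support correlation 0.1/0.2/0.3), with a = 0.4 SD.
- Under the imbalance rule, b is about 0.05 / 0.12 / 0.23.
- All Baron & Kenny steps, with a direct effect of 0.3-0.4 SD: false mediation is 9-11% / 33-43% / 63-79%, against 2-3% when all three covariates are always entered.
- With no effect on quality of life: 0.4-1.6% under the rule.
- With family support as the only link (stability 0.5, family-support correlation 0.2, direct effect 0.4 SD): b is 0.047, and all steps pass in 10.4% of trials under the rule against 2.5% adjusted.

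**The case against.** **The plan does not exclude baseline values.** A reader might infer that pre-camp values are kept out unless the arms differ. The text says imbalanced variables will be added, not that others will be left out. It also says Baron & Kenny is the main method rather than the only one, and that preliminary correlations will help settle the model. This stands: the gap is in what is specified. The only stated default is still the wrong one for this path.

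**The planned method has a guard.** A reader might take 83-92% as the false mediation rate of the planned analysis. It is not. It omits the total-effect step of Baron & Kenny, and that step brings the rate to about 4-5% when PLASMA does nothing for quality of life. The guard fails, however, when PLASMA works by another route. An improvement in quality of life is the primary hypothesis, and a mechanism would be reported in just that case.

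**The size rests on assumed correlations and a one-visit, raw-score model.** This stands. One cell (r = 0.4, s = 0.5) implies a trait correlation of 0.4/0.5 = 0.8, which is high. Sections 1 and 7.2 speak of improvement over time and longitudinal processes, so change scores are possible. In the stable-trait model they remove the bias (b about 0.00, two-path rate 4-6%). In the second model they leave b at about 0.07-0.09, slightly worse than no adjustment in the weak scenario. The plan does not say which form it will use.

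**Not every pre-camp value may exist.** Section 4.1 item (k) places spirometry at the camp and 15 months after it, so a pre-camp FEV1 cannot be assumed. Table 1 is not legible enough in the text available to settle this.

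**The stakes are limited.** Aim 2 concerns mechanism and uses exploratory outcomes. That is why this is offered as an improvement.

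**Conclusion.** The point holds as a free or cheap improvement. Aim 2 states no baseline adjustment, and the one rule that could supply it responds to a condition irrelevant to mediator-outcome confounding. Analysed as written, the mediator path absorbs stable differences between teens.

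The direction is clear, but the size depends on correlations the documents do not give. False mediation is a risk rather than a certainty: it needs PLASMA to move the mediator (with no such effect, the two-path rate under the rule was 1-3%) and, under the full method, a significant total effect. A reader might also infer that the primary comparison is compromised, or that adjustment would settle the matter. Neither follows. Aim 1 does not use the mediator path, and pre-camp scores measure the underlying traits with error, so some confounding remains.

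**What to change.** Add to Aim 2 in Section 10.1:

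- Every Aim 2 model (treatment to mediator, mediator to PAQOL given treatment, and the multiple-mediation step) includes the teen's pre-camp mediator value and pre-camp PAQOL, T1 family support, age group, sex and site, whatever the baseline balance. Pre-camp values are the mean of T1 and T2 where both are available.
- For FEV1, a pre-camp value is used only if one is collected. Otherwise the model adjusts for the remaining covariates and the limitation is stated.
- Indirect effects are reported as conditional on no residual mediator-outcome confounding, ideally with a sensitivity analysis for unmeasured confounding.
- The text states whether Aim 2 uses follow-up scores or change scores, and at which visit or visits.

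The cost is plan wording, a few degrees of freedom, some imputation where T2 is missing, and smaller, less favourable indirect effects. Apart from the FEV1 question, no new data collection is needed.

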2. CHARACTERISTICS OF STUDY POPULATION

2.1 Subject Characteristics

Asthma and its morbidity disproportionately affect minority children of low-income families in inner cities, where asthma severity has increased and poses serious challenges to achieving adequate asthma control.⁵ Disparate burdens of asthma and its adverse outcomes among minority children have been consistently documented in the past 20 years.^{4, 23-25} In 2010, asthma prevalence in black children under 18 years was twice that of white youths; children in families below the poverty threshold as defined by the US Census Bureau were 1.5 times more likely to report current asthma than those in families at or above 200% of the poverty line.² Compared with white youth, black inner-city children are 4 and 3 times more likely to have asthma-related ED visits and hospitalizations respectively.⁴ The three cities where the study will take place, Buffalo, NY; Baltimore MD; Memphis TN demonstrate high rates of pediatric asthma, high health care utilization and high morbidity and mortality rates, thus this study will take place in these cities that are most likely to benefit from a proposed intervention.

a) Number of Subjects:

A total of 378 adolescents (12-17 years) and 42 adolescent peer leaders (16-20 years) will be recruited for this study. The sample size (N=378) is based on the power analysis using a novel method developed by Roy et al.²⁶ for a 3-level hierarchical longitudinal design based on the program "RMASS." This method has the advantage of incorporating three levels from the sites and repeated-measures from each subject with random-effects of the time trends at both the subject- and site-level, which are assumed to be equivalent in terms of sampling proportions, number of groups and differential attrition rates over time. In this proposed study, quality of life, the primary outcome, was used to estimate the sample size. Using data from the previous study,²⁷ the longitudinal trajectories of quality of life and its treatment-by-time interactions based on subject-level randomization were modeled: the estimated treatment*time interaction coefficient was 0.6 units, estimated SDs for error was 15, and the random-slope was 1.76. These estimated values with a Type-I error rate (alpha) of .05 yielded a total sample size of 276 that would detect a

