utilize a well developed and detailed training manual for adolescents ("Let's Talk about Asthma") that addresses four components of asthma self-management in adolescents, including symptom (1) prevention, (2) monitoring and (3) management; and (4) communication/psychosocial empowering.²⁹ The manual meticulously covers these four areas based on the National Asthma Education and Prevention Program (NAEPP) guidelines²⁸ and presents information in a way that increases developmental and contextual relevance to inner-city adolescents. Eligible peer leaders will be recruited via referrals or from local churches or colleges using newspaper ads or flyers. A total of 42 peer leaders (14 in each site) will be trained using a structured asthma self-management manual developed by the study team. Training strategies will involve didactic sessions, discussion, demonstrations, and role-play. A certified asthma educator, who will be trained by the PI to be the peer leader trainer, will lead a 3-day training program (4 hours/day) for all three sites. Our previous study demonstrated the adequacy of the format, length and frequency of the training sessions to cover essential training components. Training content includes: Day 1: Asthma basics and prevention; Day 2: Asthma monitoring and management; Day 3: Communication/ psychosocial issue management/leadership training/hands-on practice in simulated peer-led group settings (role-play). Peer leader training will be offered no earlier than one month prior to the scheduled peer-led camp to maximize retention of acquired information and skills. Peer leaders will be evaluated using a combination of oral and written tests at the end of each session to ensure mastery and proficiency of covered content. If a trainee is absent from a session, she or he will attend an individual make-up session; anyone missing two days of training will be disqualified. In our earlier study,³⁰ peer leaders' knowledge, self-efficacy and other asthma outcomes showed declining trends 6-months post-camp, suggesting the need for a booster training session. Booster training has been recommended due to its proven benefits for peer leaders.^{31, 32} The peer leader trainer will offer a half-day booster session at 6-months post-camp at each site.

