Self-reported (standardized questionnaires) and physiological (PEFR and Spirometry) data collected longitudinally (21 months) will capture systematic and dynamic processes by which the program modifies adolescents' self-management behaviors and health outcomes. The long-term observation will also allow the investigators to examine the sustainability of the intervention. Inclusion of multiple cognitive factors (knowledge, attitude, self-efficacy, and outcome expectations) as mediators will allow us to demonstrate intricate interrelationships or mechanisms between the intervention and asthma outcomes including asthma control and quality of life in adolescents. This study will also systematically investigate the economic impact (e.g., healthcare utilization, prescription and indirect costs) of the intervention, which will offer invaluable data to policy makers who might consider adopting the intervention as a standard care for teens with asthma. Moreover, this multi-site study involving three cities representing the Northeastern, Eastern and Southern sections of the US will provide evidence of the generalizability of the intervention and its impacts, which could further accelerate the adoption and implementation of the program to address the serious health threats of asthma in inner-city adolescents and to contain economic costs to society.

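### As worded, Aim 4 has no peer-leader level; followed literally, the standard error of the leaders' time trend is in general wrong, in a direction the documents do not settle

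*Combined protocol and SAP*

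**What the plan says.** Section 10.1 gives Aim 1 a three-level model "where level 1 represents repeated measures, level 2 = subject, and level 3 = site". Aim 4, in the same section, is to be tested with the "multi-site hierarchical two-level linear mixed-effects models described in the analysis for Aim 1, with level 1 representing longitudinal measurements and level 2 sites".

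The sample-size text in section 2.1(a) describes a method with "random-effects of the time trends at both the subject- and site-level". Its variance inputs are "estimated SDs for error was 15, and the random-slope was 1.76", with no time unit for the slope and no intercept SD between persons.

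The hypothesis for Aim 4 in section 1 is that "the peer leaders (n=42) will report significant improvement in quality of life (primary outcome) and secondary outcomes" over a 15-month period. Section 4.1 gives the number: "A total of 42 peer leaders (14 in each site) will be trained". The assessments there are at enrolment, then "3 months later (T2), immediately following the camp (T3), and at 3-, 6-, 9-, 12-, and 15-months post-camp (T4-T8"). Section 7.2 gives the total span: "data collected longitudinally (21 months").

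**The concern.** Aim 4 cites the Aim 1 model, but Aim 1 describes no two-level model, and its level 2 is the subject, not the site. An analyst cannot follow both sentences. In going from three levels to two, Aim 4 removes the unit that generates the repeated measurements and keeps the one with only three members. Nothing else in the available text gives Aim 4 a leader random effect, a within-leader residual covariance or robust standard errors.

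The section 1 hypothesis for leaders is one of statistical significance, so its p-value and confidence interval depend on the standard error of the leaders' time trend. Leaving out leader intercepts puts stable differences between leaders into the residual and makes that standard error too large, so real improvement can be missed. Leaving out leader slopes ignores that leaders improve at different rates and makes it too small, so false positives rise. The planning text itself expects time trends to differ between persons.

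**Working it through.** The plan states no sample size, power or standard error for Aim 4, so there is no figure to reproduce. The question is how far the literal model's standard error departs from the correct one.

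**Inputs from the documents.** n = 42 leaders; error SD 15 (variance 225); slope SD s1 = 1.76 (s1² = 3.098). The last two are the campers' planning values, because none are given for leaders.

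**Assumptions.** Leader intercept SD at mid-follow-up s0 = 10, 15 or 20; linear trend; complete data; site intercepts but no site slopes; two-sided z test at 5%. The slope of 1.76 is taken first per visit, then per month.

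**Windows.** The 15-month hypothesis matches camp to last follow-up, T3 to T8: k = 6 visits, 3 months apart. All of T1 to T8 is also possible: k = 8, and equal 3-month spacing gives the 21 months of section 7.2. Section 4.4 puts leaders and campers on one payment schedule that starts at baseline.

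**Formulas**, with Sxx the sum of squared deviations of the visit times:

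- Correct variance of the mean slope: (225/Sxx + s1²)/42
- Literal variance, no leader level: (225 + s0² + s1²·Sxx/k)/(42·Sxx)
- Actual type I error: 2[1 − Φ(1.96 × literal SE / correct SE)]
- Setting the two variances equal gives the break-even s0 = s1·√(Sxx(1 − 1/k))

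**One case in full** (T3 to T8, per visit, s0 = 15). Sxx = 17.5. Correct: (12.857 + 3.098)/42 = 0.380, SE 0.616. Literal: (225 + 225 + 9.035)/735 = 0.625, SE 0.790. The ratio is 1.28, so the test runs at 1.2%.

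| Window | Slope unit | Sxx | Correct SE | Literal SE at s0 = 10/15/20 | Type I error | Break-even s0 |
|---|---|---|---|---|---|---|
| T3–T8 | visit | 17.5 | 0.616 | 0.674/0.790/0.929 | 3.2%/1.2%/0.3% | 6.7 |
| T3–T8 | month | 157.5 | 0.328 | 0.248/0.283/0.327 | 13.9%/9.1%/5.1% | 20.2 |
| T1–T8 | visit | 42 | 0.449 | 0.440/0.514/0.603 | 5.5%/2.5%/0.8% | 10.7 |
| T1–T8 | month | 378 | 0.297 | 0.172/0.194/0.220 | 25.5%/20.0%/14.5% | 32.0 |

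**Two variations, on T1 to T8.** If 1.76 is a variance (the wording favours an SD), break-even falls to √1.76 × √(42 × 7/8) = 8.0 per visit and √1.76 × √(378 × 7/8) = 24.1 per month. If the literal model also has a site random slope, simulation with no true site variation (20,000 runs per cell) gives 4.2%/2.3%/1.0% per visit and 12.8%/11.0%/9.1% per month. Errors in both directions remain possible.

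**The case against.** The strongest reply is that this is a wording slip. The same section makes the subject level 2 for Aim 1, the planning text has person-level trends, and section 10.1 promises preliminary analyses to settle the model. The Aim 1 notation is also missing from the available text and might show a within-person covariance that Aim 4 inherits. Both points stand as limits on certainty, and they are why the conclusion is conditional on the literal reading. They do not remove the contradiction: Aim 4's own list of levels leaves out the leader, and a promise to choose a model later does not specify one.

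A second reply is that the figures prove little. They rest on an intercept SD that the documents do not give and on campers' variances applied to specially nominated leaders. That is right; they are an illustration only.

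A reader might infer from the monthly T1–T8 row that false positives would reach 25%. The documents do not support that. It needs the monthly unit, no site slope, a low intercept SD and a window longer than the 15 months hypothesised. On T3 to T8 the same assumptions give 13.9%, and the per-visit reading makes the test conservative.

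**Conclusion.** The point holds as a contradiction in the specification. If Aim 4 is followed as worded, and no within-leader covariance comes from the unseen notation, the standard error for the leaders' trend is in general wrong and correct only at break-even. The direction is undetermined, because it turns on a between-leader intercept SD and a slope time unit that the documents do not give. Under the stated assumptions, actual type I error on the 15-month window runs from about 0.3% to 13.9%, and on all eight visits from about 0.8% to 25.5%.

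A reader might also infer that the trial's main result is at risk. It is not. Aim 4 is an uncontrolled analysis of 42 leaders, while the randomised comparison in Aim 1 has its subject level stated. The correction should be made, but its importance is moderate.

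**What to change.** Restate Aim 4 as a linear mixed-effects model with level 1 = repeated measurements and level 2 = peer leader, and state the within-leader covariance. A random intercept with a random time slope would serve, and so would an unstructured covariance. Say how the three sites enter; a fixed site effect is one option. These are choices for the trial statistician; the essential step is to name the leader as the unit of repeated measurement. It would help to state there the time coding and which assessments make up the 15-month period.

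The cost is a sentence or two in section 10.1. It needs no new data and changes nothing in Aim 1.
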